7.8.3 Vital signs

The analyses of vital signs (blood pressure and pulse rate) will be descriptive in nature. Descriptive statistics of absolute values and change from baseline from vital signs over time (see [Section 6.7](#)) will be provided.

Unscheduled measurements of vital signs will be assigned to planned time points in the same way as described above for laboratory data. However, for vital signs, descriptive statistics will be calculated by planned time point based on the last value of the subject at that planned time point (or assigned to that planned time point).

Clinically relevant findings in vital signs data will be reported as baseline conditions (prior to first administration of study treatment) or as AEs (after first administration of study treatment) if judged clinically relevant by the investigator, and will be analyzed as such.

7.8.4 ECG

Relevant ECG findings will be reported as relevant medical history/baseline condition (if a condition already exists before first administration of study treatment) or as AE (if condition emerges after first administration of study treatment) and will be summarized as such. No separate listing or analysis of ECG findings will be prepared.

7.8.5 Others

Physical and neurological examination findings will be reported as relevant medical history/baseline condition (if a condition already exists before first administration of study treatment) or as AE (if condition emerges after first administration of study treatment) and will be summarized as such. No separate listing or analysis of physical or neurological examination findings will be prepared.

Suicidality assessment

Suicidality monitoring will be performed as described in Section 5.2.4 of the CTP, results will only be listed. No further analysis will be prepared. Findings will also be reported as AEs.

Visual test

Visual test will be performed as described in Section 5.2.3 of the CTP.

Unscheduled measurements of visual tests will be assigned to planned time points in the same way as described above for laboratory data. However, for visual tests, descriptive statistics

will be calculated by planned time point based on the last value of the subject at that planned time point (or assigned to that planned time point).

Colour discrimination test

Abnormal findings during the screening examination will lead to exclusion of the subject. Any deterioration during the study compared to baseline will be reported as an AE. Results from all measurements will also be listed and summarized in a frequency table for each eye.

Visual acuity test

Any deterioration during the study compared to baseline will be reported as an AE. Results from all measurements will be listed and summarized including change from baseline separately for each eye.

Amsler grid test

Abnormal findings during the screening examination will lead to exclusion of the subject. Any deterioration during the study compared to baseline will be reported as an AE. Results from all measurements will also be listed and summarized for each eye.

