6. GENERAL ANALYSIS DEFINITIONS

6.1 TREATMENTS

For basic study information on treatments to be administered, assignment of treatment groups, and selection of doses, cf. Section 4 of the CTP.

Each subject is planned to be treated in two subsequent treatment periods in a fixed sequence order. There will be no washout-period between the two treatment periods.

Part 1:

All subjects will receive a single dose of BI 425809 alone in Visit 2 and a single dose of BI 425809 after multiple dosing of donepezil in Visit 3.

Table 6.1: 1 Dosage and treatment schedule part 1

Treatment	Substance	Formulation	Unit strength	Dosage	Total dose
A (Reference 1)	BI 425809	Tablet	25 mg	1 tablet (Day 1, Visit 2)	25 mg
B (Test 1)	Donepezil	Tablet	5 mg	1 tablet (Day 1-7, Visit 3) q.d. 2 tablets (Day 8-28, Visit 3) q.d.	245 mg
	BI 425809	Tablet	25 mg	1 tablet (Day 22, Visit 3)	25 mg

Part 2:

All subjects will receive a single dose of donepezil alone in Visit 2 and then a single dose of donepezil after multiple dosing of BI 425809 in Visit 3.

Table 6.1: 2 Dosage and treatment schedule part 2

Treatment	Substance	Formulation	Unit strength	Dosage	Total dose
C (Reference 2)	Donepezil	Tablet	5 mg	2 tablets (Day 1, Visit 2)	10 mg
D (Test 2)	BI 425809	Tablet	25 mg	1 tablet (Day 1-24, Visit 3) q.d.	600 mg
	Donepezil	Tablet	5 mg	2 tablets (Day 10, Visit 3)	10 mg

For statistical analyses of AEs, vital signs, safety laboratory data and visual tests the following separate analysis phases will be defined for each subject:

Table 6.1: 3 Analysis phases for statistical analysis of AEs, vital signs, safety laboratory data and visual tests, part 1

Study analysis phase	Label	Start	End
Screening	Screening part 1	Date of informed consent	Date/time of first administration of BI 425809
On treatment BI 425809	BI part 1	Date/time of first administration of BI 425809	Date/time of first administration of donepezil
On treatment donepezil	Don part 1	Combination of two phases: First phase: Date/time of first administration of BI 425809 + 11*24h (i.e. REP of BI425809 of 11 days) Second phase: Date/time of second administration of BI 425809 + 11*24h (i.e. REP of BI425809 of 11 days)	Combination of two phases: First phase: Date/time of second administration of BI 425809 Second phase: Date/time of last administration of donepezil + 15*24h (i.e. REP of donepezil of 15 days) or 00:00 a.m. on day after subject's trial termination date whatever occurs earlier

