6.7 BASELINE, TIME WINDOWS AND CALCULATED VISITS

Baseline is defined as the last available value before first drug administration.

Time windows are defined in Section 6.1 of the CTP. Adherence to time windows will be checked at the RPM.

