7.8.2 Laboratory data

The analyses of laboratory data will be descriptive in nature and will be based on BI standards "Display and Analysis of Laboratory Data" (9).

Analyses will be based on normalised values, which means transforming to a standard unit and a standard reference range. The original values will be analysed if the transformation into standard unit is not possible for a parameter.

Descriptive statistics of absolute values and change from baseline from laboratory parameters over time (see [Section 6.7](#)) will be provided. Frequency tables of changes between baseline and last value on treatment with respect to the reference range will be presented.

Unscheduled measurements of laboratory data will be assumed to be repeat measurements of the most recent scheduled measurement (e.g. for follow-up or confirmation of a particular value). Therefore, unscheduled measurements will be assigned to the planned time point of the previous scheduled measurement. Descriptive statistics will be calculated by planned time point based on the worst value of the subject at that planned time point (or assigned to that planned time point).

Possibly clinically significant abnormal laboratory values are only those identified either in the Investigator's comments or at the RPM at the latest. It is the Investigator's responsibility to decide whether a lab value is clinically significant abnormal or not. Standard or project-

specific rules for flagging clinically significant values in an automated manner will not be applied in this study.

Clinically relevant findings in laboratory data will be reported as baseline conditions (prior to first administration of study treatment) or as AEs (after first administration of study treatment) if judged clinically relevant by the investigator, and will be analyzed as such.

Results from the fecal occult blood testing will be listed only.

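### SAP 7.8.5 sends a visual test triggered between first dose and end of trial back to the screening time point, so the by-time-point table can show an on-treatment result as a screening result

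*SAP*

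**What the plan says.** **Schedule.** In both parts the Flow Chart attaches footnote 13 (visual tests) only to the screening and EOT rows. Protocol 5.2.3 gives the same schedule and adds tests after a visual adverse event or where the investigator finds one necessary.

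**Assignment.** SAP 7.8.5: "Unscheduled measurements of visual tests will be assigned to planned time points in the same way as described above for laboratory data". The rule it borrows is in SAP 7.8.2: "Unscheduled measurements of laboratory data will be assumed to be repeat measurements of the most recent scheduled measurement", and therefore "unscheduled measurements will be assigned to the planned time point of the previous scheduled measurement".

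**Value used.** For laboratory data the statistics are "based on the worst value of the subject at that planned time point". For visual tests they differ: they "will be calculated by planned time point based on the last value of the subject at that planned time point", and this includes values assigned to that time point. The colour test paragraph adds: "Results from all measurements will also be listed and summarized in a frequency table for each eye".

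**Baseline and phases.** SAP 6.7: "Baseline is defined as the last available value before first drug administration". SAP 6.1: "For statistical analyses of AEs, vital signs, safety laboratory data and visual tests the following separate analysis phases will be defined"; Tables 6.1:3 and 6.1:4 then end the Screening phase at the first dose. SAP 6.1 leaves technical details to an ADS Plan, which is not among the documents.

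**The concern.** Carrying an unscheduled value back makes sense when it is a recheck of a recent scheduled one. Laboratory data and vital signs have scheduled measurements throughout treatment, so this is usually a fair description. Visual tests have none between first dose and EOT. A test done because a subject reports blurred vision on drug is not a repeat of screening, yet the rule labels it as one.

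Protocol 1.2.1.3 reports transient visual disturbances at BI 425809 doses of 25 mg once daily and above, and 25 mg is the dose used here. Visual tests are a named safety parameter (protocol 2.2.2.2). The table would present a symptomatic on-drug result as pre-treatment. An abnormal colour or Amsler result in the screening row would also look like a breach of exclusion criterion 29 when there was none.

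**Working it through.** No power or error-rate calculation applies. The check is whether any scheduled visual test lies between first dose and EOT, and what the rules then do with a triggered test. EOT days are read on the Visit 3 day scale.

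**1. Time from first dose to EOT**

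| | Part 1 | Part 2 |
|---|---|---|
| Visit 3 Day d on the Visit 2 scale | d + 8 | d + 15 |
| Last dose of the multiple-dose drug | Day 28: 28 + 8 − 1 = 35 days after first dose | Day 24: 24 + 15 − 1 = 38 days after first dose |
| Residual effect period | 15 days (donepezil) | 11 days (BI 425809) |
| End of on-treatment time | 35 + 15 = 50 days | 38 + 11 = 49 days |
| SAP 6.1 planned phase durations | 8 + 28 + 14 = 50 days | 15 + 19 + 15 = 49 days |
| EOT window (Visit 3 days) | 44–49 | 36–40 |
| EOT, days after first dose | 51–56 | 50–54 |
| Scheduled visual tests from first dose until EOT | 0 | 0 |

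The end of on-treatment time agrees with the SAP's own durations. In a completer, EOT falls after it, so every on-treatment visual test is unscheduled.

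**2. Where the rule puts such a test.** The previous scheduled visual test is screening; there is no other candidate. Screening may be as early as Day −21, which is 21 days before Day 1. The longest gap between the screening test and its supposed repeat is 56 + 21 = 77 days (Part 1) or 54 + 21 = 75 days (Part 2). Counting only to the end of on-treatment time, it is 50 + 21 = 71 or 49 + 21 = 70 days.

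**3. What the table shows.** Under the last-value sentence the triggered result replaces the screening result. If the wording about all measurements governs and the carry-back still applies, the screening row holds both. Either way it contains an on-treatment result. Since baseline stays pre-dose, an acuity change from baseline could appear in the screening row.

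**4. Size for one subject.** SAP 7 bases percentages on all subjects in the set. With the planned numbers, one abnormal colour or Amsler result gives 1/18 = 5.6% (Part 1) or 1/14 = 7.1% (Part 2). Because criterion 29 excludes abnormal screening results, 0% is expected.

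**5. Why a last value would not suit a summary by phase.** Some phases join two windows (Visit 3 days):
- Don + BI part 1: Days 1–4 and 22–33 (3 + 11 = 14 days), with 22 − 4 = 18 days between the windows.
- BI part 2: Days 1–10 and 25–35 (9 + 10 = 19 days), with 25 − 10 = 15 days between the windows.

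A normal test weeks later could replace the symptomatic one.

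**6. Same rule elsewhere.** In Part 1 the pre-dose safety laboratory is on Day −3 to −1 and the next is at 96 h, so an unscheduled sample in those 96 h is carried back to before dosing. Vital signs on Visit 2 Day 1 are taken at −10 h (Part 1) or −2 h (Part 2) and next at +4 h. In Part 2 that gap overlaps the donepezil maximum at about 3–4 h (protocol 1.2.2). The first Part 1 dose is BI 425809 alone, so the point about donepezil does not arise there.

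**The case against.** The strongest counter-argument is that phase and planned time point are two separate labels. SAP 6.1 assigns visual tests to phases by actual dosing date and time, so a triggered result could carry an on-treatment phase together with a nominal screening time point. It would then not appear as screening data in a display by phase. The SAP does not fix the table layout, and the ADS Plan might settle the matter. That reading is possible, but SAP 7.8.5 states that the statistics are by planned time point and does not say that the phases override this. Protocol 7.3.4 assigns measurements by treatment at their planned time, which could carry the wrong label into the phase as well. An unseen technical plan cannot be assumed to reverse explicit SAP text.

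Second, the impact is small. Deteriorations are reported as adverse events and assigned to the correct phase, all results are listed, and the pharmacokinetic endpoints are untouched. This stands, and it limits the point to one descriptive table.

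Third, the 77 and 75 days run to the last permitted EOT day. That is fair; 71 and 70 days are the limits for a result strictly on treatment.

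Fourth, one sentence barring post-dose values from pre-dose time points would cure the mislabelling, and the choice of worst value is a preference. The first part is right. The summary value still has to be chosen once triggered tests are grouped by phase, and the joined windows argue against the last value.

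**Conclusion.** The concern holds. As written, SAP 7.8.5 places every visual test triggered between first dose and EOT at screening. In a completer that covers the whole 50 (Part 1) or 49 (Part 2) days of planned on-treatment time. A single abnormal colour or Amsler result would appear as 5.6% or 7.1% abnormal at screening.

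This rests on reading the EOT days on the Visit 3 scale and on the SAP text without the ADS Plan. The number of triggered tests is not given; with none, the table is correct. A subject who stops early may have the EOT test while still on treatment, and that test is placed correctly. Baseline, EOT change from baseline, listings, adverse event reporting and the primary analysis are unaffected. It should be corrected because the stated rule produces a wrong tabulation and the repair is cheap.

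**What to change.** 1. In SAP 7.8.2, 7.8.3 and 7.8.5, state that a measurement taken after the first dose of trial medication is never assigned to a planned time point before that dose.
2. In 7.8.5, restrict the screening summary of visual tests to pre-dose values.
3. In 7.8.5, summarise triggered post-dose visual tests by actual date and time under the phases of Tables 6.1:3 and 6.1:4. Per subject and phase, use the worst value for acuity and any abnormal result for the colour and Amsler tests. Add a footnote that these subjects are selected by symptoms.
4. For laboratory data and vital signs, show values that would otherwise be carried back before the first dose in a separate row for unscheduled measurements after first dose.

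The cost is a few sentences of SAP text and minor programming. The drawback is a few sparse extra rows from a symptom-selected group, which the footnote addresses.

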10. HISTORY TABLE

Table 10: 1 History table

Version	Date (DD-MMM-YY)	Author	Sections changed	Brief description of change
Final	20-SEP-2019		None	This is the final TSAP
